16.2.2. Secondary outcomes

Binary outcomes will be compared using an analogous method to that described under the primary outcome.

Non-ophthalmologic continuous, or pseudo-continuous outcomes collected only once post-baseline will be displayed as change from baseline and will be analysed using a linear regression model adjusted for baseline where appropriate. Results will be presented as adjusted mean differences with 95% confidence intervals. Statistical significance of a difference between treatment arms will be assessed based on the model.

Non-ophthalmologic continuous, or pseudo-continuous outcomes where the outcome is collected at multiple timepoints post-baseline (including patient reported outcome measures) will be assessed for differences between arms using mixed effect repeated measures models using linear patient trajectories through time (alternative analytical functions of time may be considered as necessary). In the initial model, a treatment by time interaction effect will be included in the model. If this is not significant, it will be considered that the treatment effect is constant over time, and models without the treatment by time interaction term will be fitted. Results will be presented as adjusted mean differences and 95% confidence intervals.

Ophthalmologic continuous, or pseudo-continuous outcomes (OCT outcomes) may have data collected in more than one eye. To best use this and increase statistical efficiency while accounting for the non-independence and high correlation between eyes within individuals, we will use hierarchical models to nest observations within patients. These models will have adjustments for treatment allocation and group-level effects for the effect of eye within participant. The presence of a linear predictor and slope-varying terms will be dependent on the number of post-baseline observations. The presence of a treatment effects will also be tested by a likelihood ratio test against a nested model with no treatment variable and otherwise identical model specification.

Ordinal outcomes will be analysed akin to the continuous outcomes however will be compared between treatment arms using ordered logistic regression models.

Data pertaining to exploratory outcomes will be summarised descriptively and/or graphically using methods appropriate to the data type. Exploratory outcomes will be presented separately for each of the (randomisation) questions (R2a, R2b, R2c, SA3a, SA3b).

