4.1. Inclusion criteria

- Confirmed diagnosis of IIH as defined by the IIH consensus criteria¹⁵.
- Age \geq 18 years.
- No evidence of sight threatening papilloedema requiring urgent surgical intervention.
- Presence of papilloedema in at least one eye measured by OCT RNFL.
- BMI greater than or equal to:
 - 30.0 kg/sqm or
 - 27.0 kg/sqm with IIH associated with increased weight or
 - 27.0 kg/sqm and of South Asian, Chinese, other Asian, Middle Eastern, Black African or African Caribbean ethnicity*.
- At least one self-reported unsuccessful dietary effort to lose body weight
- Able to provide written informed consent.

*Self-reported ethnicity according to the 2021 UK government census.

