6.5.1. Randomisation method

Participants will be randomised at the level of the individual in a 1:1 ratio to either Tirzepatide or standard of care. The randomisation process for initial randomisation R1 will use a minimisation algorithm to ensure balance in the treatment allocation for the following variables:

- Baseline acetazolamide status (currently taking, yes/no)

To avoid the possibility of the intervention allocation becoming predictable, a random element will be included in the algorithm. Full details of the randomisation specification will be stored in a confidential document at BCTU.

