16.1. Sample size

Examination of various IIH datasets held (including the IIH:WT trial²⁵, the IIH:Life cohort, and our previously published clinical trials in IIH²⁶) suggest it is anticipated that in the population of patients who receive standard of care only 5% will have resolution of papilloedema (100% reduction in the excess elevation of the optic nerve swelling). Further analysis of these datasets revealed that in those who achieved at least a 12% reduction in body weight, between 30 and 50% had a complete resolution of papilloedema. For the purposes of the sample size calculation, we have taken a conservative estimate of 37% (the median estimate).

With a type I error of 0.05, a type II error of 0.1 (corresponding to a power of 90%), a responder rate in the control arm of 5% and responder rate of 37% in the Tirzepatide arm, a sample size of 32 participants per arm is required. Inflating this to account for 25% attrition (for missing data and withdrawal) would require 43 patients per arm (86 overall).

After 50% of the planned sample size has been recruited and treated (i.e. at the end of the first randomisation R1), an assessment of the missing data is planned to ensure the levels observed fall below that assumed during this calculation, with the option to increase the sample size based on this if needed. This trial has been powered to answer the primary question for R1 only. The subsequent questions remain unpowered. This remains a limitation, however powering for these questions would result in a trial sample size that was infeasible. The purpose of these questions is to provide some high-quality evidence.

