16.2. Analysis of outcomes

A separate Statistical Analysis Plan will be produced and will provide a more comprehensive description of the planned statistical analyses. A brief outline of the planned analyses is given below.

Unless reported otherwise, the threshold for determining statistical significance from hypothesis testing will be represented by a p-value of <0.05. Where parametric tests have been specified dependent on the normality of data distribution, this will be assessed using appropriate graphics (for example histograms and q-q plots) prior to application of the test. Where randomisation is minimised by stratification variables, the main estimators will be adjusted for such variables for the primary outcome at stage R1.

Data pertaining to outcome measures will be transformed as per user manuals and standard practice to derive clinically meaningful indices where relevant.

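### The OCT models name no baseline RNFL term, and acetazolamide adjustment is stated for the primary outcome only, so the continuous R1 secondary comparisons give up precision that costs nothing to keep

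*Protocol*

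**What the plan says.** Protocol section 16.2.2 treats continuous OCT outcomes separately. It uses hierarchical models so that both eyes can contribute, giving statistical efficiency as the reason, and names the terms: "These models will have adjustments for treatment allocation and group-level effects for the effect of eye within participant". Time terms depend on how many post-baseline observations there are. Treatment is tested against a nested model that differs only in leaving out treatment. No baseline term is named.

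In the same section, non-ophthalmologic continuous outcomes measured once after baseline are adjusted for baseline where appropriate.

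Section 6.5.1 minimises the R1 allocation on one factor, whether the participant is taking acetazolamide at baseline. On the use of minimisation factors in the analysis, section 16.2 says "the main estimators will be adjusted for such variables for the primary outcome at stage R1".

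Section 9.1 has RNFL measured at screening and reported to the Trial Office before randomisation. The schedule in section 10 places one OCT in R1 after baseline, at month 6. Section 8.1.2 lists change in papilloedema by OCT as a secondary outcome. Section 4.1 requires "Presence of papilloedema in at least one eye measured by OCT RNFL".

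**The concern.** How swollen an eye is at entry is likely to predict how swollen it is at 6 months. A model without that value leaves explainable variation in the residual and widens the confidence interval. With one scheduled post-baseline scan in R1, repeated measures cannot recover the loss. The OCT outcomes are also the continuous outcomes closest to the primary endpoint, and the section's stated aim for them is efficiency.

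The acetazolamide point is similar. A factor used to balance allocation belongs in the analysis. If it is prognostic, leaving it out tends to give standard errors that are too large. Section 16.2 states the adjustment for the primary outcome only, and the continuous secondary models do not name it.

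**Working it through.** **The plan's own figure.** Section 16.1 assumes 5% type I error, 90% power and "a responder rate in the control arm of 5% and responder rate of 37% in the Tirzepatide arm", and concludes that "a sample size of 32 participants per arm is required". Taking the test as two-sided (not stated), with pooled variance and no continuity correction:

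- Mean rate = (0.05 + 0.37)/2 = 0.21.
- n = [1.960 × √(2 × 0.21 × 0.79) + 1.282 × √(0.05 × 0.95 + 0.37 × 0.63)]² / 0.32² = (1.129 + 0.679)² / 0.1024 ≈ 31.9, so 32 per arm (power 90.1%).
- With 25% attrition, 32/0.75 = 42.7, so 43 per arm and 86 overall.

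The figure reproduces. It concerns the primary outcome without covariates, so nothing below changes it.

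**Baseline adjustment of the OCT outcome.** Let r be the correlation between baseline and 6-month RNFL, with equal SD σ at both times and n per arm. The variance of the treatment difference is:

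- 6-month value, unadjusted: 2σ²/n
- change score, unadjusted: (2σ²/n) × 2(1 − r)
- baseline-adjusted: (2σ²/n) × (1 − r²)

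The adjusted model therefore has (1 + r)/2 of the change-score variance and 1 − r² of the 6-month-value variance. The documents give no r; 0.3 to 0.8 is an assumed range. The last three columns give the difference detectable with 90% power at 32 evaluable per arm, in units of σ: (1.960 + 1.282) × √(2/32 × variance factor), treating each participant as one value.

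| r | Adjusted vs change score | Adjusted vs 6-month value | Detectable: 6-month value | Detectable: change score | Detectable: adjusted |
|---|---|---|---|---|---|
| 0.3 | 0.65 | 0.91 | 0.81 | 0.96 | 0.77 |
| 0.5 | 0.75 | 0.75 | 0.81 | 0.81 | 0.70 |
| 0.7 | 0.85 | 0.51 | 0.81 | 0.63 | 0.58 |
| 0.8 | 0.90 | 0.36 | 0.81 | 0.51 | 0.49 |

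The variance falls by 10-35% against a change score and by 9-64% against the 6-month value. Because section 8.1.2 defines the outcome as change, the first range is the more relevant.

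Equal SDs matter. Suppose resolving swelling made the 6-month SD 0.7 of the baseline SD, with r = 0.5 (both assumed). In units of the baseline variance, the change score has 0.49 + 1 − 2 × 0.5 × 0.7 = 0.79 and the adjusted model 0.49 × 0.75 = 0.3675. The ratio is 0.47, a cut of about 53%.

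**Which eyes enter.** If a share f of participants have one affected eye, all contribute both eyes with equal weight, and unaffected eyes cannot improve, the average eye-level effect is multiplied by 1 − f/2. That is 0.95 at f = 10%, 0.90 at 20% and 0.75 at 50%. The documents give no f.

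**Primary model, for comparison.** Section 16.2.1 counts missing outcomes as failures, so with 25% missing the expected responders number about 32 × 0.05 + 32 × 0.37 = 13.4. A simulation (3,000 runs, 32 per arm, penalised logistic fit with marginal standardisation, RNFL added to a treatment-only model) used assumed odds ratios of 2, 3 and 5 per SD of RNFL. The variance of the risk difference fell by about 6%, 9% and 19%. Power rose by about 1, 2 and 4 points from about 92-93%.

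**The case against.** The strongest objection is that section 16.2 calls itself a brief outline and leaves detail to the SAP, where covariate lists and eye-selection rules normally sit. The repeated-measures paragraph for non-ophthalmologic outcomes names no baseline term either, and the single-measure paragraph adjusts only where appropriate. The gap may therefore be brevity rather than a decision to exclude. This stands as a caution about intent. It does not remove the point, because the OCT paragraph lists the terms of its model, and an SAP that followed it would inherit the omission.

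A second objection is that a change score already uses baseline. That is true, and it narrows the loss to 10-35% under the stated assumptions, but does not remove it.

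Three stronger readings are tempting, and the documents do not support them:

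- A reader might infer that unaffected fellow eyes are in the OCT models and dilute the effect. The protocol says only that more than one eye may supply data. Section 4.1 is an entry rule, not a rule about which eyes are analysed.
- A reader might call the primary model deficient for lacking baseline RNFL. Adjusting for the minimisation factor alone is an acceptable pre-specified choice. It is unbiased under randomisation, and its confidence interval allows for chance imbalance. With about 13 expected responders, a further covariate is a matter of judgement.
- A reader might say that no secondary outcome is adjusted for acetazolamide. Binary secondary outcomes follow a method analogous to the primary one, which arguably carries the adjustment. The gap is clear only for the continuous outcomes.

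**Conclusion.** The point holds for the continuous R1 secondary outcomes. As written, the OCT models omit a covariate available on every participant. The likely cost is 10-35% of the variance against an unadjusted change score, or 9-64% against an unadjusted 6-month value. Both ranges rest on assumed correlations of 0.3 to 0.8 and equal SDs, neither of which the documents supply. The loss is of precision; the comparison remains unbiased.

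Limiting the acetazolamide adjustment to the primary outcome is a smaller gap of the same kind, and its size cannot be worked out from the documents. Which eyes enter the OCT models is unstated and needs a sentence, but any dilution cannot be sized because the share of participants with one affected eye is not given. The primary analysis and the sample size of 86 stand as they are.

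**What to change.** In section 16.2.2, add each eye's own screening RNFL as a continuous covariate in the OCT models. With that term included, the treatment estimate is the same whether the response is the 6-month value or the change, so the choice between them no longer matters.

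In section 16.2, extend the acetazolamide adjustment to the continuous R1 secondary models, and say explicitly that it also applies to the binary ones.

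In the OCT paragraph, state whether only eyes with papilloedema at baseline enter the models or all measured eyes do.

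Baseline RNFL in the primary model may be considered as an option, but it is not needed to correct the plan.

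The cost is a wording change in the protocol, carried into the SAP before outcome data are seen. No new measurement or participants are needed.

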3.1.2. Stage R2

[figure not shown]
After 6 months, stage R1 will end and participants will have a 6 month follow up appointment. Their papilloedema will be reviewed and they will be re-randomised and enter stage R2 if they could still potentially benefit from Tirzepatide:

- Participants who have resolution or partial resolution of papilloedema as measured by OCT after 6 months of treatment with Tirzepatide plus standard of care will be randomised again to either Tirzepatide plus standard of care vs standard of care. This will allow evaluation of the maintenance of effect compared to those who discontinue treatment at 12 months. Discontinuing will enable evaluation of the impact of drug cessation on weight change and its impact on IIH at 12 months, compared to those continuing Tirzepatide plus standard of care.
- Participants who have no resolution of papilloedema as measured by OCT after 6 months of treatment with standard of care will be randomised again to either Tirzepatide plus standard of care or standard of care for 6 months. This will allow evaluation of the effect of delayed initiation of weight loss induced by Tirzepatide for 6 months on IIH, again at 12 months, compared to standard of care.

Participants will not be randomised again if they are unlikely to benefit from Tirzepatide:

- Participants who have no resolution of papilloedema after 6 months of Tirzepatide plus standard of care will not be eligible to be re-randomised as their IIH symptoms are unlikely to benefit from a second 6-month course of treatment.
- Participants who have resolution of papilloedema after 6 months of standard of care will not be eligible to be re-randomised as their IIH symptoms would not benefit from weight loss and starting Tirzepatide.

Participants who receive Tirzepatide in stage R2 will leave the trial after this 6 month treatment period.

Figure 3: Trial Schema

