3.1.2.1. Objective of stage R2

The purpose of stage R2 is threefold, meeting the secondary objectives of evaluating:

- The maintenance of effect (by continuing Tirzepatide) (R2a),
- The lasting benefit and extent of recurrence rate of papilloedema upon treatment cessation (R2b)
- The effect of delayed start to weight loss (R2c)

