9.4. Review and treatment allocation visit R2 (month 6)

With sufficient notice before the 6 month time point, an OCT scan will be arranged at a participating Specsavers UK store of the participant's choice, to be completed <2 weeks before the 6 month time point.

Then, at 6 months, a full review as per the baseline visit as detailed in **section 9.2** (minus height, demographics and medical history) will be carried out.

Once the OCT scan has been analysed by the trial researcher and all month 6 assessments have been completed, participants will be classed as responder, partial responder or non-responder.

- Responders to standard of care will leave the trial.
- Non-responders to Tirzepatide will proceed to their final follow up visit (**section 9.6**).
- Responders and partial responders to Tirzepatide, and partial and non-responders to standard of care will be re-randomised into R2 as per the R1 randomisation method in **section 6**.

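### Stage R2 is built to make randomised comparisons at month 12, but section 16.2.2 plans no between-arm estimate for them, and the only listed randomisation factor omits R1 arm and month-6 response

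*Protocol*

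**What the plan says.** Protocol section 3.1.2 gives the reason for the second randomisation. For Tirzepatide responders and partial responders it states: "This will allow evaluation of the maintenance of effect compared to those who discontinue treatment at 12 months". It describes stopping in the same comparative way, against those who continue, and delayed start against standard of care.

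Section 3.1.2.1 splits this into three labels, R2a (continuing), R2b (stopping) and R2c (delayed start), and introduces them with "The purpose of stage R2 is threefold, meeting the secondary objectives of evaluating". Section 2.1.3 lists the same aims as exploratory, and section 8.1.3 lists the month-12 and month-18 outcomes as exploratory.

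Section 16.2.2 says that exploratory outcomes are summarised descriptively and/or graphically, and then: "Exploratory outcomes will be presented separately for each of the (randomisation) questions (R2a, R2b, R2c, SA3a, SA3b".

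On allocation, section 9.4 covers Tirzepatide responders and partial responders, and then "partial and non-responders to standard of care will be re-randomised into R2 as per the R1 randomisation method". Section 6.5.1 describes that method for R1, with one listed factor: "Baseline acetazolamide status (currently taking, yes/no". It places full details in a confidential specification. Section 6.3 states a single 1:1 allocation for both groups entering R2.

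**The concern.** A randomised stage earns its value from the contrast between its arms. Section 16.2.2 lists the two arms of the continue-or-stop randomisation as separate items, in the same list as the single-arm SA3 questions. It names no difference and no interval for any of them. The participants who stay on standard of care and serve as the control for R2c do not appear in the list.

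Participants enter the continue-or-stop randomisation because their month-6 OCT showed a response. Some will look worse at month 12 whatever they receive, through measurement error, regression to the mean and the natural course of the disease. A recurrence rate in the stop arm alone cannot separate these from the effect of withdrawal. The concurrent continue arm can, but only if the two are contrasted.

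The label also decides the analysis. Under section 16.2.2 a secondary outcome gets a modelled comparison with a 95% interval, and an exploratory one gets a description. Calling the R2 aims secondary in one section and exploratory in another leaves it unclear which applies.

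The allocation point is separate and smaller. R1 arm decides which R2 question a participant answers, and full versus partial response at month 6 is a plausible driver of recurrence. Neither is listed as a factor.

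**Working it through.** **Inputs.** Section 16.1 gives "a responder rate in the control arm of 5% and responder rate of 37% in the Tirzepatide arm", alpha 0.05, power 90%, 25% attrition, and 32 per arm inflated to 43 (86 overall). Section 6.3 gives R2 entry: responders and partial responders from Tirzepatide, partial and non-responders from standard of care, 1:1. The partial-response rate on Tirzepatide is not given. I assume 0% to 63%, where 63% = 100% − 37% makes every other participant a partial responder. Losses after month 6 are not counted and would shrink the numbers further.

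**The plan's own figure.** Two-sided, pooled variance under the null, mean rate 0.21:

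n = [1.96·√(2·0.21·0.79) + 1.282·√(0.05·0.95 + 0.37·0.63)]² / 0.32² = (1.129 + 0.679)² / 0.1024 = 31.9, so 32 per arm (power 90.1%). Then 32/0.75 = 42.7, so 43 per arm and 86 in all. The stated figures reproduce. No size or precision is stated for R2.

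**Design against analysis.**

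| Label | Contrast described in 3.1.2 | Between-arm estimate in 16.2.2 |
|---|---|---|
| R2a, continue | against those who stop | none |
| R2b, stop | against those who continue | none |
| R2c, delayed start | against standard of care (no label) | none |

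**Size and precision of continue versus stop.** Let N be 32 (evaluable) or 43 (all). Pool = 0.37N + (partial rate)·N, each term rounded; per arm n = pool/2. The 95% half-width for a risk difference with both rates near 50% is 1.96·√(0.5/n); for example, n = 6 gives 1.96·√0.0833 = 0.57. The split columns assume that only total R2 allocation is balanced, ignoring R1 arm. Entrants are then the pool plus 95% of N from standard of care (30 or 41), half go to each arm, and the split within the pool is hypergeometric.

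| N | Assumed partial rate | Pool | Per arm | Half-width (points) | 60:40 split or worse | 2:1 split or worse |
|---|---|---|---|---|---|---|
| 32 | 0% | 12 | 6 | ±57 | 31% | 31% |
| 32 | 20% | 18 | 9 | ±46 | 37% | 13.5% |
| 32 | 40% | 25 | 12.5 | ±39 | 28% | 3% |
| 32 | 63% | 32 | 16 | ±35 | 7% | 0.5% |
| 43 | 0% | 16 | 8 | ±49 | 38% | 14% |
| 43 | 20% | 25 | 12.5 | ±39 | 31% | 4% |
| 43 | 40% | 33 | 16.5 | ±34 | 16% | 2% |
| 43 | 63% | 43 | 21.5 | ±30 | 8% | 0.2% |

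**R2c.** 30 to 41 entrants, so 15 to 20.5 per arm: 1.96·√(0.5/15) = 0.36 and 1.96·√(0.5/20.5) = 0.31.

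**What an uneven split costs.** The standard error scales with √(1/a + 1/b). For 5:11 against 8:8: √(0.291/0.250) = 1.08. For 4:8 against 6:6: √(0.375/0.333) = 1.06. So the loss is about 6% to 8%.

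**Imbalance on response class.** Suppose the pool divides evenly (or as nearly as it can) but response class is not a factor. The chance that the share of full responders differs by 20 points or more between arms is then about 22% to 62%, for assumed partial rates of 20% to 63%. The 62% arises at 9 per arm, where a 7:5 division of 12 full responders already gives 2/9 = 22 points.

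**The case against.** Section 16.2.2 speaks of questions, not arms, and section 3.1.2 words each question comparatively. The unlabelled R2c control fits this reading: if labels were arms, that group would be reported nowhere. On that reading both arms appear side by side and the contrast is preserved. Section 16.2 also calls itself a brief outline, the statistical analysis plan may add a difference with an interval, and section 16.1 openly says that the later questions are unpowered. This stands in part. The protocol does not say that R2b will be shown without R2a, so a reader who infers that only before-after series will be reported goes further than the text. But section 3.1.2.1 defines R2a and R2b by arm, and neither reading supplies an estimate. Lack of power is disclosed and is no error; an interval needs no power claim.

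A reader might also infer that leaving out R1 arm and response undermines R2 as a randomised comparison. It does not. Both are fixed before the second randomisation, so continue versus stop among those re-randomised from Tirzepatide is valid without them, and nothing says that the two entering groups are pooled for analysis. The cost is balance and precision. Nor should the chance of a bad split be overstated. Coin-toss allocation among full responders alone gives 21% for 5:11 or worse of 16 and 39% for 4:8 or worse of 12. Balancing total R2 allocation lowers these to 14% and 31%, and partial responders enlarge the pool. The confidential specification may already name further R2 factors.

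**Conclusion.** The point holds as a mismatch between design and stated analysis, with a lesser point on allocation. Section 3.1.2 justifies R2 by comparisons at month 12; section 16.2.2 plans description by label and no between-arm estimate or interval. The comparison is small, about 6 to 21 per arm for continue versus stop, with half-widths of about ±30 to ±57 points. It is imprecise but can be estimated, and it protects the recurrence question from regression to the mean.

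On allocation, the listed factor leaves a 7% to 38% chance of a 60:40 or worse split in the continue-or-stop pool. A meaningful difference in the mix of full and partial responders is also possible. This affects balance and precision, not validity.

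These sizes rest on the protocol's 37% and 5% rates, an assumed partial-response rate of 0% to 63% (20% to 63% for response mix), and R2 allocation balanced only in total. The statistical analysis plan and the randomisation specification were not available and may already settle part of this; the protocol wording should still be brought into line. The primary R1 analysis is unaffected.

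**What to change.** - **Section 16.2.2.** For R2a versus R2b among those re-randomised from the Tirzepatide arm, and for R2c versus its concurrent standard-of-care arm, report the between-arm risk difference or mean difference at month 12 with a 95% confidence interval. Adjust for the month-6 value where the outcome allows. Label these exploratory and make no significance claims. Keep before-after summaries for SA3, which has no concurrent control.
- **Sections 6.5.1 and 9.4.** State the factors that apply at R2. Add R1 arm and month-6 response class as stratification or minimisation factors, or confirm that the randomisation specification already has them.
- **Sections 2.1.3 and 3.1.2.1.** Use one label, exploratory, for the R2 objectives.

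The cost is wording and one setting in the randomisation system, made before the first participant enters R2. No extra data or participants are needed. The downside is that the published intervals will be wide, which fairly shows how much R2 can say.
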